Complication	
Complications will be defined according to the Clavien-Dindo classification system.¹
 
Grade I: Any deviation from the normal postoperative course without the need for pharmacological treatment or surgical, endoscopic, and radiological interventions. Allowed therapeutic regimens are: drugs as antiemetics, antipyretics, analgetics, diuretics, electrolytes, and physiotherapy. This grade also includes wound infections opened at the bedside.
 
Grade II: Requiring pharmacological treatment with drugs other than such allowed for grade I complications. Blood transfusions and total parenteral nutrition are also included.
 
Grade III: Requiring surgical, endoscopic, or radiological intervention
 
Grade IIIa: Intervention not under general anesthesia
 
Grade IIIb: Intervention under general anesthesia
 
Grade IV: Life-threatening complication (including CNS complications)* requiring IC/ICU management
 
Grade IVa: Single organ dysfunction (including dialysis)
 
Grade IVb: Multiorgan dysfunction
 
Grade V: Death of a patient

Medtronic Business Restricted

This document is electronically controlled

CONFIDENTIAL 056-F275 Rev E Clinical Investigation Plan Template

	
NOTE 1: If the patient suffers from a complication at the time of discharge (see examples in Appendix 18.1), the suffix "d" (for "disability") is added to the respective grade of complication. This label indicates the need for a follow-up to fully evaluate the complication.
 
NOTE 2: *Brain hemorrhage, ischemic stroke, subarachnoidal bleeding, but excluding transient ischemic attacks. CNS, central nervous system; IC, intermediate care; ICU, intensive care unit.

Other	

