Nephrectomy	20%	55	The mean effect size is 0.029 with a 95% confidence interval of 0.022 to 0.038. The 95% prediction interval is 0.017 to 0.047. The 99% prediction interval is 0.014 to 0.058. A performance goal of 0.20, while greater than the predicted interval, broadly aligns with the upper limits for each nephrectomy study with a comparable study size (95% upper limits ranging from 0.100 to 0.539) and is clinically appropriate. A performance goal of 0.20, assuming a sample size of up to 55 (with 10% attrition n=49), one-sided alpha of 0.008 (Bonferroni Correction), and mean effect size of 0.029, results in a power of 95%.
Prostatectomy	20%	55	The mean effect size is 0.029 with a 95% confidence interval of 0.016 to 0.051. The 95% prediction interval is 0.004 to 0.173. The 99% prediction interval is 0.002 to 0.316. A performance goal of 0.20 (20%), is clinically appropriate. A performance goal of 0.20, assuming a sample size of up to 55 (with 10% attrition n=49), one-sided alpha of 0.008 (Bonferroni Correction), and mean effect size of 0.029, results in a power of 95%.
Cystectomy	45%	31	The mean effect size is 0.162 with a 95% confidence interval of 0.132 to 0.198. The 95% prediction interval is 0.047 to 0.354. The 99% prediction interval is 0.024 to 0.520. A performance goal of 0.45 (45%), is clinically appropriate. A mean effect size of 14.1% is used in the sample size calculations as it is more aligned with internal assumptions of the performance of Hugo. A performance goal of 0.45, assuming a sample size of up to 31 (with 10% attrition n=27), one-sided alpha of 0.008 (Bonferroni Correction), and mean effect size of 0.141, results in a power of 83%.

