Endpoint	Procedure Type	PG	Rationale
Rate of subjects with complications (through 30 days)	Nephrectomy	30.0%	The mean effect size is 0.116 with a 95% confidence interval of 0.087 to 0.152. The 95% prediction interval is 0.048 to 0.252. A performance goal of 0.30 is clinically appropriate for descriptive comparison.
	Prostatectomy	45.0%	The mean effect size is 0.056 with a 95% confidence interval of 0.038 to 0.082. The 95% prediction interval is 0.006 to 0.372. A performance goal of 0.45 is clinically appropriate for descriptive comparison.
	Cystectomy	85.0%	The mean effect size is 0.417 with a 95% confidence interval of 0.272 to 0.577. The 95% prediction interval is 0.080 to 0.854. A performance goal of 0.85 is clinically appropriate for descriptive comparison.
Operative time (min)	Nephrectomy	255 min	The mean effect size is 170.1 with a 95% confidence interval of 155.5 to 184.7. The 95% prediction interval is 81.9 to 304.9. A performance goal of 255 minutes is clinically appropriate for a descriptive comparison.
	Prostatectomy	340 min	The mean effect size is 190.6 with a 95% confidence interval of 169.7 to 211.5. The 95% prediction interval is 96.9 to 324.8. A performance goal of 340 minutes is clinically appropriate for a descriptive comparison.
	Cystectomy	500 min	The mean effect size is 376.2 with a 95% confidence interval of 315.9 to 436.6. The 95% prediction interval is 185.6 to 682.1. A performance goal of 500 minutes is clinically appropriate for a descriptive comparison.
Intraoperative estimated blood loss (mL)	Nephrectomy	490 mL	The mean effect size is 181.0 with a 95% confidence interval of 131.5 to 230.5. The 95% prediction interval is 34.3 to 507.7. A performance goal of 490 mL is clinically appropriate for a descriptive comparison.
	Prostatectomy	500 mL	The mean effect size is 193.3 with a 95% confidence interval of 168.2 to 218.4. The 95% prediction interval is 54.7 to 486.5. A performance goal of 500 mL is clinically appropriate for a descriptive comparison.

Medtronic Business Restricted

This document is electronically controlled

CONFIDENTIAL 056-F275 Rev E Clinical Investigation Plan Template

Medtronic Expand URO Clinical Investigation Plan

MDT19051EINURO

Version 9.0

Page 74 of 111

Medtronic

Endpoint	Procedure Type	PG	Rationale

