	Cystectomy	500 mL	The mean effect size is 133.0 with a 95% confidence interval of 102.6 to 163.4. The 95% prediction interval was not able to be obtained due to a lack of data. As there are few literature cohorts available for this endpoint, the performance goals of the other two surgical cohorts were considered in setting this endpoint's performance goal of 500.
Transfusion rate	Nephrectomy	30%	The mean effect size is 0.079 with a 95% confidence interval of 0.056 to 0.11. The 95% prediction interval is 0.021 to 0.257. A performance goal of 0.30 is clinically appropriate for descriptive comparison.
	Prostatectomy	60%	The mean effect size is 0.020 with a 95% confidence interval of 0.011 to 0.037. The 95% prediction interval is 0 to 0.534. A performance goal of 0.60 is clinically appropriate for descriptive comparison.
	Cystectomy	55%	The mean effect size is 0.133 with a 95% confidence interval of 0.050 to 0.308. The 95% prediction interval is 0.004 to 0.869. While below the 95% prediction interval upper limit, a performance goal of 0.550 is better aligned for a descriptive comparison.
Rate of device-related conversion	Nephrectomy	15%	The literature search failed to identify studies that reported on device-related conversions. Device related conversions are expected to be a fraction of the total conversions. Conversion Rate = 100% - Surgical Success Rate, which has a performance goal of 85%. Thus, a 15% performance goal is assumed for conversions.
	Prostatectomy	15%	The literature search failed to identify studies that reported on device-related conversions. Device related conversions are expected to be a fraction of the total conversions. Conversion Rate = 100% - Surgical Success Rate, which has a performance goal of 85%. Thus, a 15% performance goal is assumed for conversions.
	Cystectomy	15%	The literature search failed to identify studies that reported on device-related conversions. Device related conversions are expected to be a fraction of the total conversions. Conversion Rate = 100% - Surgical Success Rate, which has a performance goal of 85%. Thus, a 15% performance goal is assumed for conversions.

Medtronic Business Restricted

This document is electronically controlled

CONFIDENTIAL 056-F275 Rev E Clinical Investigation Plan Template

Medtronic Expand URO Clinical Investigation Plan

MDT19051EINURO

Version 9.0

Page 75 of 111

Medtronic

Endpoint	Procedure Type	PG	Rationale

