30 days)	Prostatectomy	25.6%	The mean effect size was 0.062 with a 95% confidence interval of 0.005 to 0.469. The 95% prediction interval was not able to be obtained due to a lack of data, as there were only two cohorts as part of this meta-analysis. The highest literature-reported reoperation rate within 30 days was 0.156, applying a 10% absolute margin to this gives 0.256. Thus, a performance goal of 25.6% was set and deemed to be clinically appropriate.
	Cystectomy	25.6%	There was no literature found, therefore the prostatectomy performance goal was leveraged to assign a performance goal of 25.6%.
Mortality rate (through 30 days)	Nephrectomy	24.3%	Limited to two cohorts from one study, the performance goal is derived based on the individual cohort upper limits of 0.143. A value of 0.243 provides 10% margin on the upper limit, while remaining clinically appropriate.
	Prostatectomy	21%	Limited to one cohort, the performance goal is derived based on the individual cohort upper limit of 0.110. A value of 0.210 provides 10% margin on the upper limit, while remaining clinically appropriate.
	Cystectomy	35.1%	This analysis was based on 6 cohorts. As there was no variance between cohorts, the performance goal is derived based on the individual cohort upper limits of 0.040 to 0.251. A value of 0.351 provides 10% margin on the upper limit, while remaining clinically appropriate.
Rate of device deficiencies	Nephrectomy	20%	Device specific deficiencies were not reported in the literature. Recognizing that device deficiencies include those of preference and not all will impact the safety or performance of the device, a clinically appropriate performance goal of 20% has been selected.
	Prostatectomy	20%	Device specific deficiencies were not reported in the literature. Recognizing that device deficiencies include those of preference and not all will impact the safety or performance of the device, a clinically appropriate performance goal of 20% has been selected.

Medtronic Business Restricted

This document is electronically controlled

CONFIDENTIAL 056-F275 Rev E Clinical Investigation Plan Template

Medtronic Expand URO Clinical Investigation Plan

MDT19051EINURO

Version 9.0

Page 77 of 111

Medtronic

Endpoint	Procedure Type	PG	Rationale

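### Five descriptive benchmarks in CIP 14.5 (nephrectomy and prostatectomy mortality and reoperation, prostatectomy transfusion) are set above the goal of the endpoint that contains them

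*Protocol*

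**What the plan says.** **Composite goals.** CIP 14.4.2 sets the 30-day major-complication (Grade III or higher) goal at 20% for nephrectomy, 20% for prostatectomy and 45% for cystectomy. For prostatectomy the rationale reads "A performance goal of 0.20 (20%), is clinically appropriate". CIP 14.5 sets the any-complication goal at 30%, 45% and 85%. The prostatectomy row reads "A performance goal of 0.45 is clinically appropriate for descriptive comparison".

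**Component goals, all in CIP 14.5.**
- Mortality, nephrectomy: "the performance goal is derived based on the individual cohort upper limits of 0.143", then "A value of 0.243 provides 10% margin on the upper limit, while remaining clinically appropriate".
- Mortality, prostatectomy: an upper limit of 0.110 from one cohort, then "A value of 0.210 provides 10% margin on the upper limit, while remaining clinically appropriate".
- Reoperation, prostatectomy: the highest literature rate, 0.156, plus ten points. "Thus, a performance goal of 25.6% was set and deemed to be clinically appropriate". Nephrectomy and cystectomy borrow this value because no literature was found for them.
- Transfusion, prostatectomy: "A performance goal of 0.60 is clinically appropriate for descriptive comparison".

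**Grading.** CIP 12.4 (Table 7) makes death Grade V and surgical intervention Grade III. Of Grade II it says: "Blood transfusions and total parenteral nutrition are also included". Footnote 3 to CIP Table 6 restricts collection of transfusions to those associated with an adverse event.

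**Status of the goals.** CIP 14.5 and SAP 7.9.3 treat the secondary goals as aids to interpretation and not as success thresholds, and SAP 7.9.3.2 rules out hypothesis tests on them. CIP 14.1 ties study success to the primary endpoints.

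**The concern.** A part cannot be more frequent than the whole that contains it. If a subject who dies or is reoperated on counts as a major complication, a mortality or reoperation goal above the major-complication goal can never be the first to signal a problem: any rate that breaches it has already breached the wider goal.

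A benchmark that is not tested has one use, which is to help a reader judge an observed rate. As printed, a report could place mortality or reoperation within benchmark at a rate above the goal for all major complications together. For prostatectomy it could do the same for transfusion relative to complications of any grade.

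**Working it through.** **1. The plan's own figures reproduce.** The goals are 0.143 + 0.10 = 0.243, 0.110 + 0.10 = 0.210 and 0.156 + 0.10 = 0.256. For the primary safety test (n=49, goal 0.20, one-sided alpha 0.008), the largest passing count c satisfies P(X ≤ c | 49, 0.20) ≤ 0.008. This gives c=3 (attained 0.0067). Power at a true rate of 0.029 is P(X ≤ 3 | 49, 0.029) = 94.7%, against the stated 95%.

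**2. Component goal against containing goal.**

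| Pair | Nephrectomy | Prostatectomy | Cystectomy |
|---|---|---|---|
| Death vs Grade III+ | 24.3 > 20 | 21 > 20 | 35.1 < 45 |
| Reoperation vs Grade III+ | 25.6 > 20 | 25.6 > 20 | 25.6 < 45 |
| Transfusion vs any complication | 30 = 30 | 60 > 45 | 55 < 85 |

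Five of nine pairs are inverted, one is a tie, and cystectomy has no inversion.

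**3. How strict the containment is.** SAP 7.9.2.2 counts a primary safety event only if it is related to device, procedure or underlying condition/disease.
- Reoperation (SAP 7.9.3.1, row 8) carries the same relatedness limit and requires surgical treatment, which is Grade III. Containment is strict under both documents.
- Death (row 9) has no relatedness limit. Containment is strict on the CIP grading but not under the SAP, where an unrelated death falls outside the primary event.
- Transfusion (row 4) states no relatedness limit, while the any-complication rate (row 1) counts related events only. Again containment is strict under the CIP but not under the SAP.

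**4. Counts at n=55.** For primary safety, P(X ≤ k | 55, 0.20) is 0.0024 for k=3, 0.0087 for k=4, 0.0245 for k=5 and 0.0576 for k=6. The limit is therefore 3 subjects at 0.025/3 = 0.0083 and 5 at the last Holm step (0.025).

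No document says how an observed rate is to be compared with a secondary goal. SAP 7.9.3.5 reports a proportion with a 95% confidence interval, so both readings are shown: the largest count with x/55 at or below the goal, and the largest count whose Clopper-Pearson upper 95% limit lies below it.

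| Cell | Goal | By point estimate | p of that count vs 20% | By upper 95% limit |
|---|---|---|---|---|
| Nephrectomy deaths | 24.3% | 13 (23.6%) | 0.80 | 6 |
| Prostatectomy deaths | 21% | 11 (20.0%) | 0.58 | 5 |
| Reoperations, either group | 25.6% | 14 (25.5%) | 0.88 | 7 |

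At the planning n=49, the point-estimate counts are 11, 10 and 12, against a primary safety limit of 3, or 4 at the last Holm step.

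**5. Prostatectomy transfusion at n=55, by point estimate.** 0.60 × 55 = 33 subjects meet the transfusion goal (32 if it must be strictly below), while 0.45 × 55 = 24.75, so only 24 meet the any-complication goal. The literature mean printed for prostatectomy transfusion is 2.0%.

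**The case against.** **The goals decide nothing.** They are untested, success rests on the primary endpoints, and at the counts above primary safety would itself fail. This stands. A reader might infer that the trial could succeed despite such event rates, or that the success rule is wrong. The documents do not support either reading.

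**Transfusion cannot make the trial fail.** It is Grade II, outside the primary endpoint, and its containing goal is descriptive too. This stands: the link to primary safety holds for death and reoperation only.

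**Death is not always inside the primary endpoint.** This is correct under the SAP. The gap is narrow, because relatedness to the underlying condition counts and CIP 12.4 classes unassessable cases as possibly related, but containment of death should not be called strict without that qualification.

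**The large counts depend on a point-estimate comparison.** They do, and the plan does not specify one. Comparing the upper limit roughly halves them. Five prostatectomy deaths would then also be the most that primary safety allows at the last Holm step. The ordering of the printed goals does not depend on the comparison rule.

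**Reordering the goals does not align them with the exact test.** This is also true. Without the added ten points, goals of 14.3%, 11.0% and 15.6% would still allow 7 deaths (p=0.12 against 20%), 6 deaths (p=0.058) and 8 reoperations (p=0.20) of 55 by point estimate, all above the primary limit. A cap makes the benchmarks coherent and does no more than that.

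**The source cohorts may not be small.** CIP 14.5 gives the number of cohorts (one, or two from one study) and their upper limits, not their sizes, so no claim about size is made here.

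**Conclusion.** The point holds for five descriptive cells: mortality and reoperation for nephrectomy and prostatectomy, which exceed the 20% goal by 1.0 to 5.6 percentage points, and prostatectomy transfusion, which exceeds its containing goal by 15 points. It rests on the CIP grading. For reoperation it holds under the SAP derivations as well; for death and transfusion it is subject to the relatedness difference.

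The consequence is limited to interpretation. At the rates these cells tolerate, they give no warning that the containing endpoint has not already given. The size in subjects depends on an unstated comparison rule: 13, 11 and 14 of 55 by point estimate, or 6, 5 and 7 by the upper limit, against a primary limit of 3 to 5. No test, alpha allocation or success criterion is affected, and nothing follows for cystectomy.

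The plan already applies the needed logic once. CIP 14.5 reasons that device-related conversions are only part of all conversions and holds their goal at the 15% implied by the surgical success goal. The same reasoning was not carried to these five cells.

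**What to change.** In CIP 14.5, state one rule: no component goal may exceed the goal of the endpoint that contains it, as is already done for device-related conversion. Then:
- Reset the four mortality and reoperation cells for nephrectomy and prostatectomy to at most 20%. One way, using figures already printed, is to drop the added ten points: mortality 14.3% and 11.0%, reoperation 15.6% for both.
- Reset prostatectomy transfusion to at most 45%. This lies below its printed 95% prediction limit of 0.534, but the plan already accepts that for cystectomy transfusion (55% against 0.869).
- Leave the cystectomy rows and nephrectomy transfusion as they are.
- Do not describe the revised goals as matched to the pass boundary of the exact primary safety test.

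SAP 10.1 refers to CIP 14.5 for these goals, so no separate SAP table needs editing. The change needs no new data and alters no test or sample size. The cost is a small protocol edit and five secondary benchmarks that become less favourable to the device.

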14.6 Ancillary Objectives

Descriptive analyses of other pre-specified outcome measures beyond the primary and secondary objectives will be exploratory in nature and are not intended as a focus of the study for the evaluation of the study device.

The following data will be collected as applicable:

- Rate of positive surgical margins
- Lymph node yield
- Warm ischemia time
- Surgeon experience

14.7 Sample Size Determination

The sample size for the study was estimated based on the primary safety and effectiveness hypotheses.

Power calculation was performed using statistical software NCSS PASS 2023.

The effectiveness hypothesis is to test if the surgical success rate is above the performance goal. The surgical success rate is expected to be 90% or higher. A performance goal is set to be 85%. A sample size of 126 subjects will provide more than 80% power at one-sided alpha of 0.025 (with an expected rate of 95.2% or higher in this study).

Safety is also considered for sample size determination. The primary safety endpoint is the major complication rate. A statistical hypothesis with a performance goal is specified for each of the three surgery types. The performance goals are determined based on analyses of published literature by taking into account clinically meaningful margins and statistical precisions. Each individual hypothesis is adequately powered with at least 80% power at a one-sided alpha level of 0.008 with multiplicity adjustment taken into consideration. The sample sizes for the three surgery types are up to 55, up to 55 and up to 31 for Nephrectomy, Prostatectomy and Cystectomy respectively, after taking 10% attrition into account (up to 141 subjects in total).

With the consideration of both effectiveness and safety, a total of up to 141 subjects are planned to be treated in this study. Up to six study sites will be used. To keep enrollment balance, each study site will be allowed to enroll no more than 30% of the total population.

14.8 Demographics and Baseline Characteristics

The number of subjects screened, treated, discontinued during the study, as well as the reasons for discontinuations will be summarized for all centers combined and each center separately. Disposition and reason for study discontinuation will also be provided as a by-subject listing. All demographics and baseline characteristics will be summarized using descriptive statistics.

14.9 Analysis Populations

The following populations will be considered for the analysis of data for this study:

Full Analysis Set

The full analysis set (FAS) is defined as all enrolled subjects in whom the Hugo™ RAS procedure is begun, defined as the first skin incision. This is also known as a modified intent-to-treat (mITT) population. In the event that a subject is consented, but the first incision does not occur (e.g., if the subject becomes ineligible during the timeframe between consent and the procedure day), that subject will not be considered part of the FAS. The FAS will be the primary analysis set for the evaluation of the primary and secondary endpoints.

AEs will be collected from the time of consent. AEs occurring in subjects excluded from the FAS will be followed for 30 days post-consent through study exit and will be reported in a listing in the clinical study report. These AEs will not be included in the primary FAS analysis for either AE reporting or the analysis of the primary and secondary endpoints. The number and proportion of subjects experiencing each type of adverse event will be summarized by site and overall for the FAS.

Per Protocol Analysis Set

The per protocol analysis set (PPAS) is a subset of the FAS including only those subjects without any major protocol deviations. Prior to data analysis, a protocol deviation listing will be produced and sent to the clinical manager/team for review in order to verify which subjects will be excluded from the PPAS. Reasons for exclusion of subjects from PPAS will be documented and reported.

All enrolled subjects will be included in a subject disposition table indicating reasons for exclusion from the FAS and PPAS analysis sets.

14.10 Data Poolability

An assessment of data poolability of the sites will be performed using logistic regression for the primary effectiveness endpoint. A significance level of 0.15 will be considered (per FDA recommendation). Sites with fewer than five subjects will be combined into large sites to ensure statistical robustness. If the sites are found to be significantly heterogeneous with respect to the primary endpoint, additional analyses will be conducted to further assess variations across sites in baseline and procedural variables that might contribute to the variations.

